2.3. Benefit/Risk Assessment

Based on available clinical studies, application of acoustic vibration with positive end expiratory pressure to the nasal cavity is a relatively low-risk intervention. In two separate studies investigating its use for nasal congestion, no adverse events were reported in 90 subjects. In a more recent study looking specifically at patients with sinus headache, one patient noted mild epistaxis that resolved following use.

Similarly, four patients noted some mild-moderate discomfort during device use. No permanent or major adverse events were noted.

More detailed information about the known and expected benefits and risks and reasonably expected adverse events (AEs) of SinuSonic device may be found in the package insert and summary of product characteristics.

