The intercurrent events “intervention discontinuation for any reason” and “initiation of rescue medication or change in background medication (dose and product)” are addressed by the treatment condition of interest attribute. There are no remaining intercurrent events anticipated at this time.

- Population-level summary:

difference in mean changes between treatment conditions

Rationale for estimand: Facial pain is the primary complaint impacting quality-of-life in patients with sinus headache. Thus, we propose using 3 validated pain metrics to assess response to therapy. , .

Secondary estimand(s)

The clinical question of interest is for the secondary objective :

What is the difference in the proportion of sinus headache patients experiencing adverse events of pain and epistaxis between investigational SinuSonic treatment arm compared to sham control arm.

The estimand is described by the following attributes:

- Population:

Patients with Sinus Headache

- Endpoint:

Number and percent of subjects reporting pain with device use. Number and percent of subjects reporting epistaxis.

Nasal obstruction symptom evaluation (NOSE) Score change

- Treatment condition:

the investigational interventions regardless of discontinuation for any reason, with or without rescue medication or change in background medication (treatment policy strategy)

- Remaining intercurrent events:

- The intercurrent events “intervention discontinuation for any reason” and “initiation of rescue medication or change in background medication (dose and product)” are addressed by the treatment condition of interest attribute. There are no remaining intercurrent events anticipated at this time

- Population-level summary:

Difference in proportion of patients experiencing adverse event

Rationale for estimand: Safety is a secondary endpoint and will be assessed by specifically tracking incidence of pain with device use and epistaxis. These adverse events are based on prior study results.

4. Study Design

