8.1. Statistical Hypotheses

The primary objective is to demonstrate that Sinusonic device is superior to Sham control in achieving improvements in facial pain measured by facial pain VAS, and BPI-SF at 8 weeks. Thus, the null hypothesis to be tested in relation to the primary estimand is as follows:

- Null hypothesis: Sinusonic is not different from sham control with respect to the achievement of improvement in facial pain VAS, and BPI-SF at 8 weeks.

The null and alternative hypotheses corresponding to the secondary estimands are as follows:

Secondary objective [1]:

- Null hypothesis: SinuSonic device is not different from Sham control with respect to the achievement of adverse event rate at 8 weeks.

Secondary objective [2]:

- Null hypothesis: Sinusonic device is not different from Sham control with respect to device satisfaction rate at 8 weeks

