8.3.1.1. Main Analytical Approach

Statistical analysis will be conducted using SPSS version 25 (Armonk, NY: IBM Corp). Descriptive statistics such as means, range, standard deviations, frequencies, and percentages will be generated in order to present the baseline characteristics of both treatment arms. All continuous variables will be tested for normal distribution as determined by the Shapiro-Wilk test. To evaluate differences in outcome metrics between treatment arms (SinuSonic group vs sham control), paired t-tests will be used for normally distributed variables. Wilcoxon signed rank tests were used for non-normally distributed or ordinal variables. For all tests, a value of $p \leq 0.05$ will be considered statistically significant. The mean change between baseline and follow-up variables of interest will be calculated and measured against previously reported MCID thresholds when available or by using one-half of the baseline SD if not previously reported. Any missing data points will be excluded from analysis and handled similarly across all data points.

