8.4. Sample Size Determination

Approximately 60 participants will be enrolled. The sample size calculation is based on the primary efficacy estimand and its endpoint.

It is assumed that the proportion of participants achieving response for facial pain VAS is [30)% in the placebo intervention arm and [70)% in the arm receiving [intervention SinuSonic]. Using the normal approximation method for a 2-sided statistical test as described in Section 9.3.2, a study with an overall sample size of N = 60] participants will have over 90% power to detect a treatment difference between the two investigational interventions at a type-1 error level of 5%.

9. Supporting Documentation and Operational Considerations

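### The adverse-event and satisfaction hypotheses compare proportions, but the only between-arm tests the plan names are paired tests that cannot validly compare yes/no outcomes in independent arms

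*Combined protocol and SAP*

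**What the plan says.** Section 8.1 states two secondary null hypotheses: that "SinuSonic device is not different from Sham control with respect to the achievement of adverse event rate at 8 weeks", and that "Sinusonic device is not different from Sham control with respect to device satisfaction rate at 8 weeks". Section 3 defines the endpoints behind them as counts and percentages of participants: pain with device use, epistaxis, would use again, would recommend. It gives the population-level summary of the secondary (safety) estimand as "Difference in proportion of patients experiencing adverse event". Section 8.1.1 tests the primary and key secondary endpoints in a fixed order, each at 0.05, and stops at the first hypothesis not rejected.

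Sections 8.3.1 and 8.3.1.1 carry the same text. To compare the arms on outcomes they assign paired t-tests to normally distributed variables, and then: "Wilcoxon signed rank tests were used for non-normally distributed or ordinal variables". Frequencies and percentages appear there only for describing baseline characteristics.

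The one method for proportions is in Section 8.4, for the facial pain VAS response rate: "Using the normal approximation method for a 2-sided statistical test as described in Section 9.3.2". No Section 9.3.2 exists; the contents list runs from 9.2.6 to 10.

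**The concern.** The two secondary hypotheses are inferential, not descriptive, and the safety estimand is a difference in proportions. The analysis section offers nothing that estimates or tests that quantity. Both named tests need a natural pair. Participants in two randomised parallel arms have none, and the schedule of activities shows no baseline satisfaction measurement from which a within-person pair could be formed.

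The analyst must therefore either force a paired test onto unpaired people or pick another test. If the pick comes after the data are seen, the pilot suggests event counts in the region where standard tests of two proportions fall on opposite sides of 0.05. The formal safety verdict, and whether satisfaction may be tested after it, would then rest on a choice the plan does not make.

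**Working it through.** **Inputs.** N = 60, allocated 1:1 (Sections 8.4 and 4.1), taken as 30 analysed per arm with no dropout. Pilot: 29 completers, one epistaxis, and "four patients noted some mild-moderate discomfort during device use" (Section 2.3); if these are five different people, 5/29 = 17.2%. Pilot satisfaction was 86%. Sham rates for events and satisfaction are not in the documents, so a range is shown.

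**1. The plan's own figure.** Response 30% versus 70%, 30 per arm, two-sided 5%.
- Unpooled normal approximation: 0.40 / √(2 × 0.21/30) = 3.381; 3.381 − 1.960 = 1.421; power 92.2%.
- Pooled version: 89.3%.

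The stated power of over 90% therefore reproduces with the unpooled form. By exact binomial enumeration, the pooled z-test has power 89.6% and Fisher's exact test 83.8%.

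**2. The named rank test forced across arms.** Pair each active participant with a sham participant. Differences are +1, 0 or −1, all non-zero ranks are tied, and the signed rank statistic reduces to z = (x − y)/√(x + y), where x and y count the two kinds of discordant pair. For 26/30 versus 19/30:

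| Pairs with both yes | x, y | z | p |
|---|---|---|---|
| 15 | 11, 4 | 7/√15 = 1.81 | 0.071 |
| 16 | 10, 3 | 7/√13 = 1.94 | 0.052 |
| 17 | 9, 2 | 7/√11 = 2.11 | 0.035 |
| 18 | 8, 1 | 7/√9 = 2.33 | 0.020 |
| 19 | 7, 0 | 7/√7 = 2.65 | 0.008 |

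The data are the same in every row; only the arbitrary pairing differs. The paired t-test behaves alike (p from 0.006 to 0.070).

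**3. A test chosen later.** For 5/30 versus 0/30:
- Pooled z: pooled rate 5/60 = 0.0833; SE = √(0.0833 × 0.9167 × 2/30) = 0.0714; z = 0.1667/0.0714 = 2.34; p = 0.020.
- Fisher: 2 × C(30,5)/C(60,5) = 2 × 142,506/5,461,512 = 0.052.

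| Events, active v sham | Pooled z | Boschloo | Fisher |
|---|---|---|---|
| 5 v 0 | 0.020 | 0.027 | 0.052 |
| 4 v 0 | 0.038 | 0.070 | 0.112 |
| 6 v 1 | 0.044 | 0.056 | 0.103 |

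Boschloo values take the arm sizes as the fixed margins. For satisfaction, 26/30 versus 19/30 gives 0.037 (z) and 0.072 (Fisher).

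**4. How often z and Fisher disagree at 0.05.** Sum Bin(a; 30, p₁) × Bin(b; 30, p₂) over all tables where exactly one test rejects.
- Events, active 17.2%: 36.8% of trials at sham 0%, 25.0% at 3.4%, 19.7% at 5%, 8% at 10%, 3% at equal rates.
- Epistaxis alone, 3.4% versus 0%: 1.8%.
- Satisfaction, active 86%: 9.7%, 10.6% and 6.3% at sham 70%, 60% and 50%.

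**5. Cost of each choice.** At 13.8% (4/29) in both arms the true size is 5.4% for z and 1.6% for Fisher. At 17.2% versus 0%, z rejects in 78.5% of trials and Fisher in 41.7%; at 17.2% versus 5%, in 35% and 15%.

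**The case against.** **The gap may be silence, not a wrong rule.** The normality check is stated for continuous variables, so yes/no outcomes can be read as outside the rule. That is a fair reading, but it leaves two formal hypotheses with no test at all. Section 8.3.2 defers further detail to a SAP, but that sentence sits under subgroup analyses and the combined document supplies nothing more on these endpoints.

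**A stronger inference fails.** A reader might infer that the signed rank rule could declare a difference between arms with identical event rates. That would require pooling all participants and testing them against zero, ignoring arm, whereas the text is about comparing arms. With 5/30 in each arm, any forced pairing gives equal numbers of the two discordant types, and p = 1.0 wherever discordant pairs exist.

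**The disagreement rates depend on the sham rate.** The figures of 20% to 37% hold only for sham rates of 0% to 5%, and the 17.2% pools pain and epistaxis, which Section 3 lists separately. This stands, and the lower figures are shown for that reason.

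**The consequence is narrow.** Under Section 8.1.1 these tests are formal only after the primary hypothesis is rejected, and satisfaction only after a difference in adverse events as well (taking the order to be that of Section 8.1). Section 3 also lists satisfaction as tertiary. A non-significant safety test would not show safety under any of these methods. All of this stands; it limits how often the gap matters without closing it.

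**Overlap.** The same sentence misapplies paired tests to the pain scores. Replacing them with independent-sample t and rank tests would repair the scores but would still leave the small-count choice open for the yes/no endpoints.

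**Conclusion.** The point holds as a should-fix gap. Two hypotheses on proportions have no valid between-arm test, and the tests that are named give an answer that depends on arbitrary pairing (p from 0.008 to 0.071 on one fixed table). Leaving the choice until later matters at pilot-like counts: 5 versus 0 is significant by pooled z and Boschloo but not by Fisher. The disagreement between z and Fisher runs from 37% of trials down to 8% as the sham rate goes from 0% to 10%, assuming 30 per arm, no dropout and a 17.2% active rate.

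A reader might also infer that Fisher's test is the one correct answer and should govern every yes/no outcome, including VAS response. The documents do not support that. Section 8.4 rests on a normal approximation with over 90% power, and Fisher's power there is 83.8%. For the safety endpoints, Fisher's conservatism lowers the chance of flagging an excess of events. What is needed is one test fixed in advance; which one is a judgement.

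**What to change.** In Section 8.3.1.1 (and its duplicate, 8.3.1):

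- Restrict the t and rank tests to scores: VAS, BPI-SF and NOSE.
- Before unblinding, name one two-sample test of proportions for pain with device use, epistaxis, would use again and would recommend. Boschloo's exact test is one option. Fisher's is another, provided its conservatism is stated: size about 1.6% at a 13.8% rate in both arms, and lower power to detect excess events.
- Report the difference in proportions with a score-type 95% confidence interval (Miettinen-Nurminen or Newcombe). This gives the safety estimand in Section 3 the estimate it now lacks.

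In Section 8.4, replace the dead reference to Section 9.3.2 with a test consistent with the stated normal approximation. Do not point it at a Fisher rule, which would leave the section claiming power that the cited test does not have.

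Reconcile the status of satisfaction, which is tertiary in Section 3 and a secondary objective in Section 8.1.

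The cost is about a paragraph of analysis text, with no new data or participants. The real trade-off is statistical: an exact test guarantees the 5% level but gives up some power, most with Fisher.

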8.1.1. Multiplicity Adjustment

A closed testing procedure that controls the family wise error rate in the strong sense at the overall [5]% level will be applied. The statistical comparisons for the primary efficacy endpoint and the key secondary endpoints will be carried out in the hierarchical order as indicated in Section 9.1. This means that the statistical hypotheses are tested in the prespecified order at the same significance level of $\alpha = [0.05]$ as long as all preceding hypotheses are rejected. Once a hypothesis is not rejected, subsequent hypotheses cannot be formally tested and therefore cannot be rejected.

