8.3. Statistical Analyses

8.3.1. General Considerations

Statistical analysis will be conducted using SPSS version 25 (Armonk, NY: IBM Corp). Descriptive statistics such as means, range, standard deviations, frequencies, and percentages will be generated in order to present the baseline characteristics of both treatment arms. All continuous variables will be tested for normal distribution as determined by the Shapiro-Wilk test. To evaluate differences in outcome metrics between treatment arms (SinuSonic group vs sham control), paired t-tests will be used for normally distributed variables. Wilcoxon signed rank tests were used for non-normally distributed or ordinal variables. For all tests, a value of $p \leq 0.05$ will be considered statistically significant. The mean change between baseline and follow-up variables of interest will be calculated and measured against previously reported MCID thresholds when available or by using one-half of the baseline SD if not previously reported. Any missing data points will be excluded from analysis and handled similarly across all data points.

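### Sections 8.3.1 and 8.3.1.1 call every test with p ≤ 0.05 significant, Section 8.1.1 allows a rejection only while the testing sequence is unbroken, and nothing says which rule governs claims

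*Combined protocol and SAP*

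**What the plan says.** Section 8.1.1 (Multiplicity Adjustment) commits to a closed procedure that "controls the family wise error rate in the strong sense at the overall [5]% level will be applied". Hypotheses are "tested in the prespecified order at the same significance level of $\alpha = [0.05]$ as long as all preceding hypotheses are rejected". The stop rule follows: "Once a hypothesis is not rejected, subsequent hypotheses cannot be formally tested and therefore cannot be rejected". The procedure covers the primary efficacy endpoint and the key secondary endpoints, and the comparisons are to be "carried out in the hierarchical order as indicated in Section 9.1".

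Section 8.1 states three null hypotheses. The primary one concerns SinuSonic against sham "with respect to the achievement of improvement in facial pain VAS, and BPI-SF at 8 weeks". The first secondary one reads: "SinuSonic device is not different from Sham control with respect to the achievement of adverse event rate at 8 weeks". The second secondary one concerns the device satisfaction rate.

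Section 8.3.1.1 (Main Analytical Approach) closes its description of the tests with "For all tests, a value of $p \leq 0.05$ will be considered statistically significant". Section 8.3.1 (General Considerations) carries the same sentence, running on as "will be considered statistically significant. The mean change between baseline and follow-up variables of interest will be calculated". Neither place mentions Section 8.1.1, and Section 8.1.1 mentions neither of them.

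**The concern.** One rule is conditional and the other is not. They agree as long as every step succeeds, and they can part as soon as one fails. Suppose the primary comparison gives p = 0.08 and satisfaction gives p = 0.03. Section 8.1.1 permits no claim on satisfaction. The sentence in Section 8.3.1.1, taken literally, labels that result significant.

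The difference matters because the 5% family-wise guarantee comes from the condition, not from the threshold. If the flat sentence decides what is claimed, the guarantee is lost. The choice between the two readings would also be made after the results are known, unless it is settled beforehand.

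A related gap concerns endpoints with no hypothesis in Section 8.1: NOSE change, the percentage achieving an MCID, and the pain scores on Day 1 and at weeks 2, 4 and 6. For these, the flat sentence is the only significance rule the plan gives, and nothing marks their p-values as nominal.

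**Working it through.** **Inputs from the protocol.** Overall family-wise level 5% and level 0.05 at each step (Section 8.1.1). Flat threshold p ≤ 0.05 (Sections 8.3.1 and 8.3.1.1). Three null hypotheses (Section 8.1). A 2-sided test at 5% (Section 8.4).

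**Assumptions.** Each hypothesis is one two-sided z-test, all three nulls are true, and the test statistics share a common correlation ρ. The plan gives no correlation, so ρ = 0, 0.5 and 0.8 are shown.

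**Step 1: the plan's own figure.** In a fixed sequence under the global null, a false rejection requires the first test to reject. The family-wise error is therefore P(first test rejects) = 0.05, whatever the correlation. Simulation of 400,000 trials for three tests, with ρ from 0 to 0.7, gave 0.0499 to 0.0504. The stated 5% is reproduced, and using 0.05 at each step is consistent with it.

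**Step 2: the flat rule used for claims on the three hypotheses.**

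Independent tests: 1 − (1 − 0.05)³ = 1 − 0.857375 = 0.1426.

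Correlated tests, with c = 1.96:

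1 − ∫ φ(u) [Φ((c − √ρ·u)/√(1 − ρ)) − Φ((−c − √ρ·u)/√(1 − ρ))]³ du

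| Assumed ρ | Family-wise error | Multiple of 5% |
|---|---|---|
| 0 | 14.3% | 2.9 |
| 0.5 | 12.5% | 2.5 |
| 0.8 | 9.8% | 2.0 |

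**Step 3: whether the stop rule can be applied as written.**

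- Section 8.1.1 sends the reader to Section 9.1 for the order. Sections 9.1.1 to 9.1.12 hold regulatory, ethical, data-handling and safety-reporting text, and no order of endpoints.
- The key secondary endpoints are not named.
- VAS and BPI-SF share one null hypothesis, with no statement of whether both must succeed, either may, or one comes first. If either could succeed at 0.05, the first step alone would reach 1 − 0.95² = 9.75% for independent tests.
- Section 3 lists NOSE change as secondary and satisfaction as tertiary. Section 8.1 has a secondary hypothesis for satisfaction and none for NOSE.

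The 5% in Step 1 therefore depends on treating the primary as a single test and on an order that still has to be written down.

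**The case against.** The strongest reply is that there is no contradiction. Section 8.1.1 is the specific rule on claims, and it uses 0.05 at every step. The sentence in Sections 8.3.1 and 8.3.1.1 closes a general description of test methods. A hypothesis after a failed step is, under Section 8.1.1, not formally tested, so a per-test threshold need not apply to it. On that reading 0.05 is the level of each test that is reached, and both texts stand.

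That reading is sound and probably the intended one. A reader might infer more from the flat sentence: that it overrides Section 8.1.1, so that a claim after a failed step is at once permitted and prohibited. The documents do not support this. Nothing gives Section 8.3.1 precedence, and the threshold is the same number in both places. What remains is that the reconciling reading is not written down. The sentence does not describe a nominal level; it says what counts as significant, for all tests.

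A second reply is that Section 8.1.1 promises control only for the primary and key secondary endpoints, so a nominal result on any other endpoint breaches nothing. This also stands. A reader might count six tests (VAS, BPI-SF, adverse events, satisfaction, NOSE and MCID response) and arrive at about 20.7% at correlation 0.5, some four times 5%. That comparison fails. It adds endpoints that have no hypothesis in Section 8.1, and it splits a primary that the 5% baseline treats as one test. For endpoints outside the hierarchy the problem is one of labelling, not of a broken family-wise guarantee.

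**Conclusion.** The concern holds as an unresolved ambiguity in the rule for declaring significance. Two rules stand side by side with no cross-reference and no precedence. A consistent reading exists, but the plan does not state it.

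The size is conditional. If the flat rule were used for claims on the three hypotheses in Section 8.1, the family-wise error would be about 9.8% to 14.3% instead of 5%. This rests on one test per hypothesis, the global null, and an assumed correlation between 0.8 and 0. If Section 8.1.1 governs and the order is fixed, the error stays at 5%.

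Removing the flat rule would not by itself secure the 5%. The missing order and the undefined joint primary would still leave the stop rule unusable, so the two should be corrected together. The point should be settled before unblinding. It does not affect the sample size or power figures.

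**What to change.** In Sections 8.3.1 and 8.3.1.1, replace the sentence with wording such as:

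> The two-sided significance level for each test is 0.05. Statistical significance is declared only for hypotheses in the Section 8.1 hierarchy that are reached under the stop rule in 8.1.1; all other p-values are nominal and are reported with estimates and 95% confidence intervals.

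At the same time, put the explicit testing order in Section 8.1 and delete the pointer to Section 9.1. The order should say how VAS and BPI-SF are sequenced or combined, which endpoints count as key secondary, and where NOSE and satisfaction stand, in agreement with Section 3.

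The significance wording is a short replacement in two places. The testing order needs a decision by the study team as well as text. The sample size does not change. The downside is that some secondary results can no longer be called significant.

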2.3.3. Overall Benefit Risk Conclusion

Taking into account the measures taken to minimize risk to participants participating in this study, the potential risks identified in association with the SinuSonic device are justified by the anticipated benefits that may be afforded to participants with Sinus headache.

3. Objectives, Endpoints, and Estimands

Objectives	Endpoints
Primary	

 To determine superiority of SinuSonic intervention versus control in treatment of facial pain for patients with complaint of sinus headache that lack objective evidence of sinonasal inflammation 	
 Change in facial pain visual analogue scale at 8 weeks Change in Brief Pain Inventory Short Form at 8 weeks
Secondary	

 To determine safety of device use 	
 Number and percent of subjects reporting pain with device use Number and percent of subjects reporting epistaxis Change in Nasal Obstruction Symptom Evaluation (NOSE) Score at 8 weeks
Tertiary	

 To determine device use satisfaction 	
 Number and percent of subjects that would use the device again Number and percent of subjects that would recommend the device to others

Primary estimand

The primary clinical question of interest is:

What is the improvement in facial pain measured by facial pain VAS, and BPI-SF in patients with sinus headache treated with SinuSonic device versus a sham device regardless of discontinuation of investigational intervention for any reason and regardless of initiation of rescue medication or change in background medication.

The estimand is described by the following attributes:

- Population: Patients with complaint of sinus headache lacking objective evidence of sinonasal inflammation of nasal endoscopy or imaging
- Endpoint: change from baseline to 8 weeks in facial pain VAS, and BPI-SF
- Treatment condition:

the investigational interventions regardless of discontinuation for any reason, with or without rescue medication or change in background medication (treatment policy strategy).

- Remaining intercurrent events:

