4.1. Overall Design

- This is a parallel, two-arm, sham placebo controlled multicenter (Mayo AZ, Mayo FL and Mayo RST), clinical trial investigating use of the novel SinuSonic Device for sinus headache.
- The control group will be a sham device of similar appearance to the investigational device
- Participants will be healthy volunteers with complaint of sinus headache lacking objective evidence of sinonasal inflammation on exam or endoscopy
- Primary outcome measures of facial pain measured using facial pain VAS and BPI-SF will be assessed at baseline, Day 1, 2 week, 4 week, 6 week, and 8 weeks.
- Participants will be randomized in a 1:1 fashion; SinuSonic arm: Sham device, respectively.
- Total Duration of study participation will be 11 weeks; 2-3 weeks for screening and randomization and 8 weeks for the intervention component.

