5.1. Inclusion Criteria

Participants are eligible to be included in the study only if all of the following criteria apply:

1. Participant must be ≥ 18 years of age inclusive, at the time of signing the informed consent.
2. Participants who are overtly healthy as determined by medical evaluation including medical history and physical examination.
3. Capable of giving signed informed consent
4. Facial pain or pressure for ≥ 3 months of symptom duration
5. Pain/pressure VAS score of ≥ 5
6. Lund MacKay Score of ≤ 3 with no single sinus score of 2

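### The primary comparison of change in VAS and BPI-SF makes no adjustment for baseline pain; ANCOVA would cost almost nothing and may gain appreciable precision, though the documents do not fix how much

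*Combined protocol and SAP*

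**What the plan says.** Section 3 defines the primary endpoint as "change from baseline to 8 weeks in facial pain VAS, and BPI-SF" and the population-level summary as the "difference in mean changes between treatment conditions". It names no covariate.

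For the comparison between arms, Section 8.3.1.1 says "paired t-tests will be used for normally distributed variables", with Wilcoxon signed rank tests for non-normal or ordinal variables. Change scores enter that section only in one sentence, which begins "The mean change between baseline and follow-up variables of interest will be calculated" and goes on to set that change against MCID thresholds. That describes a comparison with a threshold, not the test between arms. Section 8.3.1 repeats the same text. No ANCOVA, regression or mixed model appears in Section 8, and Section 6.3 describes no stratification by baseline pain. Section 8.3.2 refers to a SAP for more detail on the statistical analysis, but the supplied text has no further SAP section.

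Baseline pain is available. Section 4.1 says that VAS and BPI-SF "will be assessed at baseline, Day 1, 2 week, 4 week, 6 week, and 8 weeks".

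**The concern.** Analysing raw change amounts to fixing the slope of the Week-8 score on baseline at exactly 1. If the true slope is lower, subtracting the whole baseline score adds noise to every participant's outcome. Any chance difference in baseline pain between arms then carries over, in part, into the estimated effect.

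Enrolment is capped at 60, so lost precision cannot be recovered by recruiting more. ANCOVA targets the same difference in mean changes with data already collected. It needs to be prespecified, because a covariate chosen after seeing an imbalance would look post hoc.

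This is separate from the paired-test wording. Paired t and signed-rank tests do not compare independent arms, which is a more serious defect in the same paragraph. Replacing them with a two-sample t-test on change would still leave baseline unadjusted.

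**Working it through.** **The plan's own figure.** Section 8.4 states over 90% power for 30% against 70% responders with N = 60, two-sided 5%.
- SE under the alternative: √(2 × 0.21/30) = 0.1183. SE under the null, pooled: √(2 × 0.25/30) = 0.1291.
- Unpooled: 0.4/0.1183 − 1.960 = 1.42, power 92.2%.
- Pooled: (0.4 − 1.960 × 0.1291)/0.1183 = 1.24, power 89.3%.

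The statement holds with the unpooled variance and is within a point with the pooled one. It concerns a responder proportion, so it says nothing about precision for the continuous change.

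**Inputs for the continuous endpoint.**
- Pilot VAS SDs, 0–100 mm, n = 29: 15.7 at baseline and 21.7 at 4 weeks (Sections 1.1, 2, 2.1 and 2.2). Using them at Week 8 is an assumption.
- 30 per arm, from N = 60 randomised 1:1, with no dropout.
- r: not in the documents, so a range is shown.
- Illustrative difference: 12 mm, which is the MCID of 1.2 in Section 7.1 read on a 0–10 scale. That section does not state the scale, and the plan does not power on this difference.

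**Formulas.**
- Change-score variance = 15.7² + 21.7² − 2r(15.7)(21.7) = 717.4 − 681.4r.
- ANCOVA variance = 21.7²(1 − r²) = 470.9(1 − r²).
- Slope b = r × 21.7/15.7, which equals 1 only at r = 15.7/21.7 = 0.72.
- One SE of baseline difference = 15.7 × √(2/30) = 4.05 mm. It shifts the change-score estimate by (1 − b) × 4.05 mm in size.
- Power from the noncentral t: 58 df for change; 57 df for ANCOVA, with its variance multiplied by 1 + 1/56 for the estimated slope.

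| r | Change variance | ANCOVA variance | Excess | Power at 12 mm, change / ANCOVA | Shift per one-SE imbalance |
|---|---|---|---|---|---|
| 0.15 | 615.2 | 460.3 | 34% | 45% / 56% | 3.2 mm |
| 0.3 | 513.0 | 428.5 | 20% | 52% / 59% | 2.4 mm |
| 0.5 | 376.7 | 353.2 | 7% | 65% / 67% | 1.3 mm |
| 0.7 | 240.4 | 240.2 | about 0 | 84% / 83% | 0.1 mm |

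The excess column omits the charge for the extra parameter. With it, the excess is 31%, 18% and 5% at r = 0.15, 0.3 and 0.5, and ANCOVA is about 2% worse at 0.7.

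**Can r be recovered from the pilot?** If changes were normal with mean 59.6 − 34.6 = 25.0 mm, and 70% exceeded 12 mm, the SD of change would be 13/0.524 = 24.8 mm. That gives r = (717.4 − 24.8²)/681.4 = 0.15. The same sum gives r = 0.04 for 20 of 29 responders, 0.35 for 21 of 29 and 0.55 for 22 of 29. One patient moves r from 0.04 to 0.35, so r is not identified.

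**The case against.** The strongest reply is that the size of the loss is unknown and may be nil. That stands. A reader might take r = 0.15 from the pilot and conclude that about a third of the variance is being wasted. The documents do not support this. The roughly 70% figure is given across all pain metrics at 4 weeks, no 12 mm threshold is stated for the pilot, and one patient changes the answer materially.

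A reader might also argue that the entry rule, "Pain/pressure VAS score of ≥ 5", forces a low slope. It does not. Selecting on baseline lowers the correlation but leaves a linear slope unchanged. Nor do the documents say that the pilot used this rule, so its baseline SD of 15.7 mm cannot be put down to it.

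Third, a change-score comparison is unbiased over randomisations. The shift from imbalance is error conditional on the observed baseline difference, and the confidence interval already allows for it on average. It is not systematic bias. This also stands.

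Last, it is fair to say that the plan never specifies a two-sample test of change: that analysis is inferred from the estimand. But no reading of Section 8 supplies a baseline covariate.

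What remains is the asymmetry. Over the range shown, ANCOVA gains up to about 11 points of power at low r and costs under one point at r = 0.7.

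**Conclusion.** The omission is clear; its cost is not. With the pilot SDs carried to Week 8, excess variance runs from about 34% at r = 0.15 to nil near r = 0.7, and the documents give no basis for choosing a value in that range. Prespecifying ANCOVA is a worthwhile, nearly free improvement, not the repair of an invalid estimator.

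The point does not undermine N = 60 or the stated power, although a reader might infer that it does. Those rest on a responder proportion, not on mean change. Equally, they give no assurance about precision for the continuous endpoint.

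**What to change.** In Section 8.3.1.1 (and its duplicate in 8.3.1):
- Replace the between-arm paired t-test with an ANCOVA of the Week-8 score on arm plus the baseline value of the same scale, for VAS, each BPI-SF score used, and NOSE.
- State which pre-device measurement is the VAS baseline. As the Schedule of Activities reads in the supplied text, VAS is marked at Screening and Day 1 but not under Baseline, while BPI-SF and NOSE are marked there.
- Report the adjusted mean difference with its 95% CI, and keep the unadjusted two-sample difference in mean change as supportive.
- Replace the signed-rank branch with a between-arm rank-based sensitivity analysis.

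The cost is wording and one degree of freedom per model. No new data or participants are needed. The same edit removes the paired-test problem.
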